9. RESEARCH INFORMATION IN MEDICAL RECORDS

N/A

10. DATA ANALYSIS AND DATA MONITORING

10.1 Planned Statistical Analysis: Analyses will be performed using SAS, and R⁵⁶ will be used as analysis software to ensure the validity and reproducibility of the results. We will perform descriptive statistics on each outcome measure to look for abnormality and outliers. If a measure is not normally distributed, transformation will be applied. We will identify and investigate outliers for sources of errors, and conduct preliminary analyses on data distribution and bivariate correlations to determine the appropriate statistical model as well as the final interpretation of the results. We will investigate missing data with pattern analysis for data missing completely at random (MCAR), missing at random (MAR) or missing not at random (MNAR), and use statistical methods appropriate for each type such as maximum likelihood and multiple imputation to impute missing values so full analysis can be performed with sensitivity. We will compute Cronbach's alphas for psychometric measures, and assess construct validity using exploratory or confirmatory factor analysis when appropriate. The PLASMA and control groups will be compared on baseline data to determine any systematic differences; if any are found, analyses will include the variables as covariates in the model to adjust for the imbalances.

Aim 1: A multi-site hierarchical three-level linear mixed-effects model,^{26, 56, 57} where level 1 represents repeated measures, level 2 = subject, and level 3 = site, will be used to analyze treatment differences and treatment-by-time interaction described in the following notation by Hedeker and Gibbons.⁵⁷

Aim 2: The mediating effects will be examined mainly using the mediation methods of Baron & Kenny.⁵⁸ When found significant, a multiple mediation analysis⁵⁹ procedure will be used to further determine whether the effect of PLASMA on quality of life is mediated jointly by multiple exploratory outcomes.

Aim 3: Moderating effects will be examined by multiple linear models and generalized linear models described in Berridge and Crouchley⁵⁶ or Chen and Peace⁶⁰ along with the above multi-site hierarchical three-level linear mixed-effects models.

Aim 4: This aim will be tested by applying the multi-site hierarchical two-level linear mixed-effects models described in the analysis for Aim 1, with level 1 representing longitudinal measurements and level 2 sites.

Aim 5: The costs of services received during visits to a physician's office, outpatient department, or ED will be estimated by taking the global relative value unit for each service CPT (Current Procedural Terminology) code multiplied by a standard conversion factor.⁶¹ Hospital charges will be converted to costs using department-specific cost-to-charge ratio.⁶² Medications and dosages prescribed will be captured; standard wholesale unit cost from the Pharmaceutical Red Book⁶³ will be used to estimate medication costs. To calculate lost productivity costs of a family with a sick teen, we will estimate total lost income related to each participant by multiplying total number of work hours missed by a parent's hourly wage. Program costs will be estimated from the actual time peer and adult leaders spent in carrying out the program multiplied by hourly earnings, costs of equipment/ supplies, and overhead costs; program time will not include staff time for research-related tasks. We will estimate the average program cost per participant by study group, and include this estimate as one component of direct healthcare costs. The

medical or general Consumer Price Index⁶⁴ will be used to inflation-adjust costs to current year prices.⁶⁴ For each teen at each time-point, we will calculate total direct costs, direct costs by major category (office visit, hospitalization), indirect lost-productivity costs, and total direct and indirect costs. For withdrawals from follow-up, we will impute missing utilization and cost data assuming a linear trend in use and cost given prior experiences, where we will estimate weighted least square regression on log-transformed cost and obtain smearing-retransformed predictions.⁶⁵ For PLASMA and control groups separately, we will calculate the cost difference between each time point and baseline for each teen, assuming (s)he received “standard care” before treatment. Cost differences for each group will be modeled against follow-up points and individual covariates to estimate the independent impacts of each program on costs relative to standard care.

10.2 Data and Safety Monitoring: The proposed project meets the NIH definition of a clinical trial and thus requires a Data and Safety Monitoring Plan. The Safety Monitoring Committee (SMC) will be established for the independent review of data. This study involves minimal risk because “the probability and magnitude of harm or discomfort anticipated in the research are not greater in and of themselves than those ordinarily encountered in daily life or during the performance of routine physical or psychological examinations or tests” (HHS.gov). Therefore, we will form the SMC. This independent committee will be charged with reviewing safety and trial progress and providing recommendations for study continuation and modification. The SMC comprises four PI-appointed members who are investigators and biostatisticians independent of the study protocol, as required by the NIH. The names and affiliations of the board members are listed below. These individuals are not participating in this project and can provide objective feedback and recommendations to the investigators regarding any issues of data safety and monitoring. All have agreed to serve on the SMC for this study. The Committee Chair elected by the board members will lead the meetings and submit any reports to the NINR if necessary. The PI will provide written reports to the SMC on the current status of the trial, interim analyses, adverse events and problems encountered. If there are recommendations for consideration (e.g., changes in sample size, modifying outcomes) or amendments to the study protocol, the PI will provide a summary to the committee for review. The PI will be responsible for disseminating the SMC recommendations to participating clinical sites and the NINR.

- [name], Associate Professor, Biostatistician/clinical trial expert, University of Rochester School of Nursing
- [name], MPH, Professor, Content/clinical trial expert, University of Rochester Medical Center, Department of Pediatrics
- [name], PhD, Professor, Biostatistician, University of Tennessee Health Science Center, Biostatistics & Epidemiology Division, Preventive Medicine Department.
- [name], MPH, Associate Professor, Clinical trial expert, Division of General Pediatrics and Adolescent Medicine, Johns Hopkins School of Medicine.

The SMC will meet annually (via video-conference). Each meeting will be divided into an open and closed session. Each meeting will be conducted by Roberts Rule of Order, and written summaries and recommendations will be sent to the PI. Necessary changes to the study protocol will be communicated within 48 hours, and changes will be made expeditiously. The open session will be attended by the members of the SMC and the study team (the PI, site-PIs, and study coordinators from each site). During the session, the PI will present general progress of the study, adverse events, subject accrual, protocol compliance, quality control and timeliness. The closed session will be attended by only the SMC members, who will discuss data presented during the open session and vote on recommendations.

NOTE: This application includes a clinical trial of a behavioral intervention that has already been registered in ClinicalTrials.gov (NCT01161225) during the PI's earlier study in complying with registration and regulatory guidelines for this designation. The registered study protocol will be updated to reflect the current study design and outcomes.

Investigator Time and Resources

This IRB protocol is in partial fulfillment of Just-in-Time (JIT) notice requirements of the National Institutes of Health, National Institute of Nursing Research, in connection with NIH grant application R01 1R01NR014451 ([name], PI). The study will be conducted only on condition of grant award notification and funding, which will ensure sufficient investigator time and resources to conduct the study. Sufficient investigator and institutional resources have been verified by the School of Nursing grants management department and the Associate Dean for Research.

REFERENCES

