Hypothesis: We hypothesize that: relative to the control group, the PLASMA group will report greater improvement over time in (H1) quality of life (primary outcome), and (H2) asthma knowledge, attitudes, outcome expectations, self-efficacy, self-management skills, and asthma control, FEV1 (exploratory outcomes). (H3) The post-PLASMA scores on outcome measures will be higher than pre-program scores from both treatment groups.

- 2) To examine the mediating effects of the secondary outcomes (knowledge, attitudes, outcome expectations, self-efficacy, self-management skills, asthma control, and FEV1) on the primary outcome (quality of life) of the intervention.
- 3) To examine the moderating effects of personal factors (e.g., age, sex, family support) on primary and secondary outcomes of the intervention.
- 4) To evaluate the effects of PLASMA on primary and exploratory outcomes in peer leaders (16-20 years).

Hypothesis: We hypothesize that the peer leaders (n=42) will report significant improvement in quality of life (primary outcome) and secondary outcomes (knowledge, attitudes, outcome expectations, self-efficacy, self-management skills, asthma control and FEV1) over the course of 15 months.

- 5) To determine the economic impact of the intervention. This aim will be accomplished by (5a) measuring the direct healthcare costs and total costs of the PLASMA program, as compared with the control group; (5b) performing net cost analyses for each type of costs; and (5c) estimating cost-effectiveness ratios of the PLASMA group compared with the control.

Hypothesis: We hypothesize that the direct and overall costs per participant in the PLASMA group will be less than costs per participant in the control group, or cost neutral.

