2. CHARACTERISTICS OF STUDY POPULATION

2.1 Subject Characteristics

Asthma and its morbidity disproportionately affect minority children of low-income families in inner cities, where asthma severity has increased and poses serious challenges to achieving adequate asthma control.⁵ Disparate burdens of asthma and its adverse outcomes among minority children have been consistently documented in the past 20 years.^{4, 23-25} In 2010, asthma prevalence in black children under 18 years was twice that of white youths; children in families below the poverty threshold as defined by the US Census Bureau were 1.5 times more likely to report current asthma than those in families at or above 200% of the poverty line.² Compared with white youth, black inner-city children are 4 and 3 times more likely to have asthma-related ED visits and hospitalizations respectively.⁴ The three cities where the study will take place, Buffalo, NY; Baltimore MD; Memphis TN demonstrate high rates of pediatric asthma, high health care utilization and high morbidity and mortality rates, thus this study will take place in these cities that are most likely to benefit from a proposed intervention.

a) Number of Subjects:

A total of 378 adolescents (12-17 years) and 42 adolescent peer leaders (16-20 years) will be recruited for this study. The sample size (N=378) is based on the power analysis using a novel method developed by Roy et al.²⁶ for a 3-level hierarchical longitudinal design based on the program "RMASS." This method has the advantage of incorporating three levels from the sites and repeated-measures from each subject with random-effects of the time trends at both the subject- and site-level, which are assumed to be equivalent in terms of sampling proportions, number of groups and differential attrition rates over time. In this proposed study, quality of life, the primary outcome, was used to estimate the sample size. Using data from the previous study,²⁷ the longitudinal trajectories of quality of life and its treatment-by-time interactions based on subject-level randomization were modeled: the estimated treatment*time interaction coefficient was 0.6 units, estimated SDs for error was 15, and the random-slope was 1.76. These estimated values with a Type-I error rate (alpha) of .05 yielded a total sample size of 276 that would detect a

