time trend over eight time points (T1-T8) between groups with a power of .80. This sample size was estimated on the assumption that the analyses use multi-site hierarchical 3-level linear mixed-effects models. In the earlier study, the attrition rate of the inner-city subsample (n=55) was 27% including those who failed to attend the camp program (n=13, 23%) and those lost to follow-up (n=2, 4%). To compensate for a possible attrition rate of 27%, the total sample size was increased to 378 (126 for each site; 63 each of two groups).

b) Gender and Age of Subjects:

Recruitment will not be limited on gender. Based on epidemiological data, we will focus on adolescents from 12-17 years of age for campers and 16-20 years of age for peer leaders.

Participants will be stratified by gender and age (younger 12-14 years, older 15-17 years), which emerged as influential covariates in the PI's earlier study. Within each of four blocks generated by each combination of these two covariates, each subject will be randomly assigned to either group using a computer-generated randomization table. Stratified randomization will ensure a similar number of subjects representing each block in the two treatment groups, balancing the influence of age and gender. Stratified randomization will be done separately for each site, and centrally coordinated and managed. Within the treatment group, participants will be assigned to subgroups based on their age [younger (12-14 years) and older groups (15-17)] to allow the study team to adjust the levels of difficulty/complexity of program content delivered at the camp. In doing so, we will attempt to enhance participants' understanding of the information covered in the program. In the previous study, we found no differences in study outcomes or camp satisfaction between gender-matched groups and co-ed groups, so subgroups will be gender-mixed.

c) Racial and Ethnic Origin:

Enrollment of participants will not be restricted to any racial or ethnic groups. By recruiting participants from three cities with high prevalence and incidence of pediatric asthma, (again based on epidemiological data) we anticipate the sample demographic to have a higher proportion of minority populations representative of the neighborhoods targeted (Buffalo, Baltimore and Memphis.)

d) Vulnerable Subjects:

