(j) Peak Expiratory Flow Rate (PEFR): we will use commercial electronic peak flow meters (Piko-1™). The Piko-1 (Ferraris Respiratory, Louisville, CO, USA) measures peak expiratory flow and FEV1, and it can store up to 96 measurements that are date- and time- stamped. Three color zones are visible on the display of the device: green for >80%, yellow for 50-80% and red for <50% of an individual's best. Stored data in the Piko-1 can be downloaded to a computer. The device is powered by batteries, lasting about 2 years if used 6 times a day. Values from the Piko-1 have shown high correlations ($r=0.93-0.95$) with those from a reference spirometer, indicating

the acceptable accuracy of the device.^{50, 51} The Piko-1 will be provided to 20 randomly selected participants from each site (10 from each treatment group) who will be instructed to use the device at least once a day. The RAs will make home visits every 3 months to download the stored data to a computer. For the rest of the sample, we will provide a manual peak flow meter with training on its use and instruct them to use it daily and record the values in a log as we proposed in the application, because this is part of self-management routines that we will attempt to reinforce through our training programs.

(k) Spirometry will be performed using a portable KoKo® spirometer (Pulmonary Data Service; Louisville, CO). Predicted values will be based on the equations of Polgar. The primary variables will be forced vital capacity (FVC) and FEV1, to be measured twice, at the camp and 15-months post-camp. Respiratory therapists at each site will be trained to perform the test in accordance with the ATS/ERS standardization of spirometry⁵² prior to conducting the tests, and data will be interpreted in collaboration with a pulmonologist at the study center.

Moderators:

(l) Perceived Family Support (PFS): We found that family support influenced quality of life and asthma control in adolescents.⁵³ This 20-item scale measures individuals' perception of their family fulfilling their needs for support, information and feedback. Construct and criterion validity was demonstrated.⁵⁴ Cronbach's α in our previous study was .85. **(m) Sociodemographic Form (SDF)** will be completed by parents to indicate adolescents' race, age, sex, insurance type, parental education and annual family income.

Table 1: Study measures for each assessment point

PRIMARY OUTCOME	PAQL	EXPLORATORY OUTCOMES												MODERATOR	

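### Gender and age group define the randomisation strata, but the visible covariate rule would bring them into the Aim 1 model only after an observed baseline imbalance

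*Combined protocol and SAP*

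**What the plan says.** Section 2.1(b) stratifies participants by gender and by age group (12-14 and 15-17 years), separately at each site. It says these factors "which emerged as influential covariates" in the earlier study, and that "Stratified randomization will ensure a similar number of subjects representing each block in the two treatment groups".

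Apart from site, which is level 3 of the mixed model, section 10.1 gives one visible rule for covariates in the treatment comparison. The arms are compared on baseline data for systematic differences and, "if any are found, analyses will include the variables as covariates in the model to adjust for the imbalances". No variable list, test or threshold is given. The sociodemographic form in section 4.1 collects "race, age, sex, insurance type, parental education and annual family income".

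Age and sex are also named as moderators in Aim 3. That is a separate question and does not place them in the Aim 1 test.

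On the primary test, the hypothesis in section 1 is that "the PLASMA group will report greater improvement over time in (H1) quality of life (primary outcome"). Section 2.1(a) sizes the trial on a trend between groups over T1-T8, for which "the estimated treatment*time interaction coefficient was 0.6 units"; no time unit is attached. Section 10.1 says the three-level model "will be used to analyze treatment differences and treatment-by-time interaction" and then refers to notation that is absent from the text available for review.

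**The concern.** The two sections work against each other. Section 2.1(b) balances the arms on the two factors it considers influential. Section 10.1 then admits a covariate only when balance has failed. The better the stratification works, the less likely its own factors are to reach the model, while any other baseline variable can enter by chance.

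Two things follow. First, the primary covariate set is settled only after data have been seen, by a comparison whose criterion is not written down. Second, an analysis that ignores factors balanced by design uses a standard error that is too large for a level comparison, so it is somewhat conservative.

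A smaller question concerns time. T1 and T2 precede the camp, so neither arm has yet been treated at those visits. The visible text does not say how a treatment-by-time term handles them.

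**Working it through.** **1. Numbers per arm.** Section 2.1(a): 276 / (1 − 0.27) = 378.1, which agrees with the stated 378. With 63 per arm at each of three sites, each arm has 189.

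**2. Would the rule select the strata?** There are 3 sites × 2 × 2 = 12 cells, and each gender (or age group) occupies 6. Suppose the arms differ by *d* participants in every cell, all in the worst direction. The shares then differ by 6*d*/189. With a share of 50% (assumed), SE = √(0.5/189) = 0.0514.

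| *d* | difference in share | z | p |
|---|---|---|---|
| 1 | 3.2 points | 0.62 | 0.54 |
| 2 | 6.3 points | 1.23 | 0.22 |
| 3 | 9.5 points | 1.85 | 0.06 |

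Even three per cell, everywhere and in one direction, would not reach 5%.

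**3. Can chance select others?** The sociodemographic form has four further items: race, insurance, parental education and income. If each is compared independently at 5% (assumed), the chance of at least one false difference is 1 − 0.95⁴ = 0.185, about 19%.

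**4. Cost for a level comparison, no baseline adjustment.** Let *R* be the share of the variance of the averaged outcome explained by gender and age group. The documents give no value; 5-10% is assumed. With these factors balanced, the true variance of the arm difference is (1 − *R*) times the variance the unadjusted test uses.
- Size = 2[1 − Φ(1.96/√(1 − *R*))], which is 0.044 at *R* = 0.05 and 0.039 at *R* = 0.10.
- Power = Φ(λ − 1.96/√(1 − *R*)), against Φ(λ − 1.96) with adjustment. Where the adjusted power is 0.80 (λ = 2.80), the unadjusted power is 0.785 or 0.769.
- The loss runs from about 0.5 point (*R* = 0.05, power near 0.95) to about 4 points (*R* = 0.10, power near 0.5).

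**5. The same with T1 and T2 used as baseline.** Inputs: error SD 15 and random-slope SD 1.76 (section 2.1(a)), subject intercept SD 10-20 (assumed), 138 per arm, and the T4-T8 mean as outcome. Baseline adjustment removes most of the covariate part, because the T1/T2 weights sum to 0.50-0.79 with time in visits and 0.76-0.90 in months. The part left is *R*(1 − sum of weights)² divided by the remaining share of variance. In the least favourable case (visits, intercept SD 10, *R* = 0.10) it is 0.10 × 0.495² / 0.753 = 0.033, giving a size of 0.046. Over the whole range the size is 4.6-5.0%, and the power lost for an effect held from the camp onward is at most about 1 point.

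**6. The treatment-by-time test.** A gender or age effect that is constant over visits cancels from each participant's slope, so with balanced data the standard error of the interaction does not change. The exception is strata that also predict individual slopes. With 10% of slope variance explained (assumed), the simulated size was 3.7% without and 4.9% with adjustment for that. The unadjusted test is again conservative.

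**7. Pre-camp visits.** Code T1-T8 as 0-7, and take a camp effect of 1 that is present from T3 and held. The mean over eight visits is 0.75 and the fitted slope is 6/42 = 0.143. The fitted line is 0.75 − 3.5 × 0.143 = 0.25 at T1 and 0.39 at T2. One straight line would thus place 25% and 39% of the effect before the camp.

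**8. Time unit.** A simple two-sided slope formula gives total N = 4(1.96 + 0.84)²(15²/Sxx + 1.76²)/0.6². In visits (Sxx = 42) this is about 737; in months (Sxx = 378) it is about 322. Reading 15 as a variance, in months, gives 274. The printed inputs do not settle 276 until the unit is known. They do not show it to be wrong either, because the sizing method also needs a site-level variance and an attrition pattern that are not printed.

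**The case against.** The strongest objection is that the Aim 1 notation, where covariates and time coding would normally appear, is missing from the available text. A reader might infer that the plan omits the strata from its primary model; that cannot be said. What stands is the rule in section 10.1. It is intact, and missing notation does not turn an imbalance-triggered rule into a prespecified one.

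Second, no permuted blocks are described, only a computer-generated table, so the cell imbalances in step 2 are assumptions. This is fair but does not rescue the rule. Even with no balancing at all, two independent 5% comparisons would flag at least one of the two factors with probability 1 − 0.95² = 9.75%.

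Third, the harm is small. This stands. A reader might infer inflated type I error or a material loss of power; the direction is conservative, and the powered term is barely touched.

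Fourth, a reader might infer from the two terms named in section 10.1 that the H1 test is open to choice after the data are seen, or that a T1-T8 slope falls short of the planned 80% power. Neither is supported. H1 and the sizing text both point to treatment-by-time, and the second term may simply be the main effect that accompanies an interaction. The 0.6 coefficient came from earlier trajectories whose shape is not given, so no shortfall can be shown. Replacing the primary term would be a trade-off. A post-camp slope, for instance, would have power of only 0.05 for a benefit that is held, and would turn negative for one that halves.

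**Conclusion.** The point holds in limited form. In the visible text, the primary covariate set depends on observed imbalance and tends to exclude the two factors used to stratify. For a level comparison the cost is a true size of 4.4-3.9% and about 0.5-4 points of power, falling to at most about 1 point after baseline adjustment. For the treatment-by-time test it is essentially nil in balanced data. These sizes rest on the assumed 5-10% of variance and, for the baseline-adjusted figures, on an assumed intercept SD of 10-20. The main gain from a change is a covariate set fixed in advance. The validity of the trial is not in question.

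The time question is minor and conditional. It needs an answer only if the missing notation does not already give one.

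**What to change.** In section 10.1:

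- State that the Aim 1 model always includes gender and age group as fixed effects, whatever the baseline comparison shows, with site kept as the plan models it.
- State that the imbalance-triggered rule is not used for the primary analysis. It may stay for sensitivity analyses.
- If the notation does not already do so, confirm that treatment-by-time is the term that tests H1, give its time unit, and say how the pre-camp visits T1 and T2 enter.

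The cost is wording and two fixed effects. No new data are needed, and the sample size is unaffected.

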4. METHODS AND STUDY PROCEDURES

4.1 Study Procedures and Assessments

Design: This study will use a two-group randomized controlled design implemented in three metropolitan cities: Buffalo, NY, Baltimore, MD, and Memphis, TN. The project coordinator and a research assistant in each city who are not involved in direct patient care of teens with asthma will be responsible for recruitment and consent process taking place in each site. Peer leaders will attend a three-day intense training session that will take place prior to camps, lead small-group instructional activities at a one-day camp (PLASMA group) and follow up their group members bimonthly for 15 months. Camp participants from each site (n=126) will be randomly assigned to the peer-led (PLASMA) group or the adult-led (control) group. Upon enrollment, participants will be stratified by gender and age (younger 12-14 years, older 15-17 years), and randomly assigned to either group within each of four blocks generated by the combination of gender and age strata. Each group will attend a separate day camp where an asthma self-management program will be implemented either by peer leaders (intervention) or healthcare professionals (control). After the camp, the intervention group will receive peer-leader contacts bimonthly for 14 months using phone calls or other communication technologies (e.g., emails, or short-message system (e.g., texting) of teens' choice. Adult instructors (healthcare professionals) will contact the control group bimonthly for 14 months using similar methods, but different contact topics.

Both groups (intervention and control – more details below) will provide data at enrollment (T1), 3 months later (T2), immediately following the camp (T3), and at 3-, 6-, 9-, 12-, and 15-months post-camp (T4-T8).

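### Site is a random level with only three units, so its variance is poorly determined and the primary test is at risk if treatment effects vary by site; Aim 4 omits the subject level altogether

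*Combined protocol and SAP*

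**What the plan says.** Section 4.1 describes a "two-group randomized controlled design implemented in three metropolitan cities: Buffalo, NY, Baltimore, MD, and Memphis, TN". Section 2.1 says these cities were picked for their high asthma burden and their likelihood of benefit, and that randomisation is stratified and run separately at each site. Both arms are therefore present in every city.

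Section 10.1 (Aim 1) specifies a linear mixed model "where level 1 represents repeated measures, level 2 = subject, and level 3 = site". The sample size method in Section 2.1(a) is described as having "random-effects of the time trends at both the subject- and site-level". Its inputs come from the previous study: "the estimated treatment*time interaction coefficient was 0.6 units, estimated SDs for error was 15, and the random-slope was 1.76". None is labelled as a site-level variance. The result is given as "Type-I error rate (alpha) of .05 yielded a total sample size of 276", for a "time trend over eight time points (T1-T8) between groups with a power of .80".

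For the 42 peer leaders, Section 10.1 (Aim 4) specifies a two-level model "with level 1 representing longitudinal measurements and level 2 sites".

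The readable text gives no degrees-of-freedom method, no rule for a zero site variance and no fixed-site alternative. Section 10.1 announces model notation that does not appear in the text version. It may have been lost in conversion, so its absence is not counted against the plan.

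**The concern.** A variance estimated from three units has 2 degrees of freedom. If the plan relies on it, three things can happen: the estimate is zero and the site level drops out unannounced; the estimate is far from the truth; or, if the treatment-by-time effect itself is random across sites, the correct reference distribution has very heavy tails.

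The last case bears on the primary hypothesis. It is plausible, because each arm has its own camp in each city, with locally chosen adult leaders and different peer leaders. Section 1 also sets generalizability across sites as a goal, yet Section 10.1 names no site-by-treatment test and no site-specific estimates to address it.

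In Aim 4 the issue is different. Up to eight measurements on one peer leader would be treated as independent within a site, which makes the standard error of the time trend wrong.

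**Working it through.** **The plan's own figures.** 276 / (1 − 0.27) = 378.1, so the inflation to 378 reproduces. The 276 itself does not follow from the literal inputs on a two-sided test (error SD 15, slope SD 1.76): it becomes 738 with visits coded 0–7, or 324 with time in months 0–21. It is reached under other unstated readings, such as 15 taken as a variance with time in months. That is a separate matter. Below, 80% power at 276 is taken as given, with two-sided alpha 0.05 (sidedness is not stated) and 276 / 6 = 46 per arm per site.

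**Calibration.** 80% power needs a noncentrality of 1.960 + 0.842 = 2.80, so SE = 0.6 / 2.80 = 0.214. With 138 per arm, SE² = 2V/138, giving V = 69 × 0.214² = 3.16 for the variance of a subject's slope.

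**Precision of a site variance on 2 df.** The 95% limits are 2/χ²(0.975) = 0.27 and 2/χ²(0.025) = 39.5 times the estimate; for the SD, 0.52 to 6.3 times.

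**Chance that the site trend variance is estimated as zero.** This is P(F(2,270) < 1/r), with r = 1 + 92 × SD²/3.16 and 92 subjects per site. For assumed true SDs of 0, 0.2, 0.3 and 0.5, r is 1, 2.16, 3.62 and 8.27, and the chance is 63%, 37%, 24% and 11%.

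**Trends common to both arms.** If site j adds a trend s to both arms, the between-arm slope difference at that site is (effect + s) − s = effect. Simulation (20,000 runs, site and site-by-time fixed) agrees: for common-trend SDs of 0, 0.5 and 2.0, power is 0.792, 0.796 and 0.800, and null rejection is 0.052, 0.051 and 0.049.

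**A treatment-by-time effect that varies by site with SD tau (assumed).** SE² = 2V/138 + tau²/3. The critical value on 2 df is t = 4.30.

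| tau | SE | Power, normal test with true SE | Power, t on 2 df | Type I error if tau is omitted |
|---|---|---|---|---|
| 0 | 0.214 | 80% | 35% | 5% |
| 0.2 | 0.243 | 69% | 29% | 8% |
| 0.3 | 0.275 | 59% | 25% | 13% |
| 0.6 | 0.407 | 31% | 15% | 30% |

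The last column applies to inference beyond these three cities.

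**Aim 4.** Inputs: 42 leaders, 8 times, error SD 15, slope SD 1.76 (variance 3.10), site fixed, and an assumed subject intercept SD of 0 to 15, independent of the slope.

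- True variance of the mean slope: (3.10 + 225/Sxx) / 42.
- Variance the model would report with no subject level: (225 + intercept variance + 3.10 × mean of t²) / (42 × Sxx).
- Visits 0–7 (Sxx = 42, mean t² = 17.5): true 0.201, against 0.158 at intercept SD 0 and 0.286 at SD 15. The ratios 1.27 and 0.70 imply rejection rates of 8% and 2%.
- Months 0–21 (Sxx = 378, mean t² = 157.5): true 0.088, against 0.045 and 0.059. The ratios 1.96 and 1.49 imply 16% and 11%; simulation gives 17% and 12%.
- A test on the 42 subject slopes holds about 5% in every case.

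**The case against.** A reader might infer that the site variance cannot be estimated at all and that the 80% power claim is simply false. The documents do not support either reading. The variance can be estimated, though very imprecisely. Section 2.1(a) names random time trends, not random treatment-by-time effects, and trends shared by the arms cancel under within-site randomisation.

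The 35% figure needs two things the readable text does not state: a site-level treatment-by-time effect, and a test on 2 df. Nor do the failures coincide: when the relevant site variance is estimated as zero, the test is close to the ordinary subject-level one. These objections stand and make the Aim 1 power concern conditional.

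A random site level can also be defended because generalizability is an explicit aim. As a choice of target this is fair. But three purposively chosen cities say little about a wider population of cities, whichever way site is modelled. A fixed interaction test does not settle it either: it describes consistency across these three, and its power has not been calculated here.

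For Aim 4, one could suppose that the subject level is implied by the reference back to Aim 1. The sentence, however, calls the model two-level and names both levels, and subject is neither. The cancellation argument does not help, since peer leaders form a single group.

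**Conclusion.** For Aim 1 the point holds in a limited form. Site as a random level with three units is a fragile choice and is not needed for the randomised comparison. If only site intercepts or common trends are random, the cost is an unstable variance estimate, and the primary contrast is essentially unaffected. If a site-level treatment-by-time effect is intended, a 2 df test has about 35% power at best, falling to 15% at an assumed site SD of 0.6. The text does not show which is meant. These figures rest on the stated 80% at 276, equal sites and assumed site SDs.

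For Aim 4 the model is wrong as written. The error can go in either direction, from about 2% to about 17% against a nominal 5%, because the time coding and the intercept SD are not given.

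**What to change.** Aim 1: fit site and site-by-time as fixed effects, with a subject random intercept and slope. State the full random-effects structure and the degrees-of-freedom method. Report treatment-by-time estimates with confidence intervals for each city, plus a 2 df site-by-treatment-by-time test, as descriptive evidence on consistency across the three cities.

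Sample size: restate the basis of 276 for that model, since Section 2.1(a) ties it to the three-level one.

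Aim 4: use a subject random intercept and slope, with site as a fixed effect.

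The cost is revised analysis wording and a restated or rerun sample size justification; no new data are needed. If 80% at 276 is accepted, power stays at about 80%. The downside is that inference is formally limited to these three cities.
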